8.1.3 Exploratory Efficacy Assessments

8.1.3.1 PAGI-SYM and PAGI-QOL

The PAGI-SYM will assess the patient's severity of symptoms related to the GI problem. The PAGI-SYM is a 20-question assessment (Rentz, 2004). The patient will circle the number that best describes how severe the symptom has been during the past 2 weeks. PAGI-SYM subscale scores are calculated by taking the mean of the items in each subscale; the subscale scores vary from 0 (none or absent) to 5 (very severe). The half-scale rule is applied for missing data (i.e., the subscale score is calculated using the mean of non-missing items; when more than 50% of items are missing, the score is set to missing). The total score is calculated by taking the mean of the subscales. If a subscale score is missing, the PAGI-SYM total score is set to missing.

If the patient has not experienced the symptom, they would circle 0. If the symptom has been very mild, mild, moderate, or severe, they would circle 1, 2, 3 or 4, respectively.

The PAGI-QOL will assess the patient's current GI problems such as pain, discomfort or other problems and evaluate how these symptoms have affected the patient's quality of life and well-being in the past 2 weeks. There are 30 questions in the assessment, with questions such as "Have you had to depend on others to do your daily activities?" and "Have you felt helpless?" with answer options including "none of the time," "a little of the time," "some of the time," "a good bit of the time," and "all of the time." The PAGI-QOL contains 30 items covering five subscales: Daily Activities (10 items), Clothing (2 items), Diet and Food Habits (7 items), Relationships (3 items), and Psychological Well-Being (8 items). Subjects are asked to respond

Version 3.0 47 of 85 20 April 2022

to each item on a 6-point Likert scale, ranging from 0 (none of the time) to 5 (all of the time). Subscale scores are calculated by averaging across the items within the specific subscale after reversing item scores. The range of scores is 0–5; higher scores indicate better HRQL (de la Loge, 2004)

In this study, the change from baseline over time for the PAGI-SYM and PAGI-QOL scores will be assessed by comparing Day 1 to Day 28. The patients will complete these assessments using an electronic diary.

8.1.3.2 CGI-S and CGI-I

The CGI-S provides an overall clinician-determined summary measure that takes into account all available information, including a knowledge of the patient's history, psychosocial circumstances, symptoms, behavior, and the impact of the symptoms on the patient's ability to function. The CGI actually comprises two companion one-item measures evaluating the following: (a) severity of psychopathology from 1 to 7 and (b) change from the initiation of treatment on a similar seven-point scale (Busner, 2007).

The CGI-S asks the Investigator the question: "Considering your total clinical experience with this particular population, how mentally ill is the patient at this time? This is rated on the following 7-point scale: 1=normal, not at all ill; 2=borderline mentally ill; 3=mildly ill; 4=moderately ill; 5= markedly ill; 6=severely ill; and 7=among the most extremely ill patients. The rating is based upon observed and reported symptoms, behavior and function in the past 7 days.

The CGI-I will ask the Investigator the question: "Compared to the patient's condition at admission to the study, this patient's condition is 1=very much improved since the initiation of study treatment; 2=much improved; 3=minimally improved; 4=no change from baseline (the initiation of study treatment); 5=minimally worse; 6=much worse; and 7=very much worse since the initiation of study treatment.

In this study, the change from baseline over time for the CGI-S and CGI-I scores will be assessed by comparing Day 1 to Day 28. The investigator will complete these assessments using an electronic diary.

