 To evaluate the effect of different doses of PCS12852 on the gastric emptying rate, as measured by the GEBT, in patients with moderate to severe idiopathic gastroparesis (IG) or DG To evaluate the PK profile of PCS12852 at different dose levels. 	 Change in gastric emptying rate from baseline as determined by the AUC of the gastric emptying rate over time as assessed by the GEBT at Visit 6 (Day 28) after administration of the PCS12852 or placebo. Change in gastric emptying rate from baseline using the t₁₀ and t₅₀ metric for gastric emptying rate. Concentrations of PCS12852 in plasma; PK parameters will be estimated from concentration-time data using noncompartmental methods, as data permit. 			
Secondary				
To evaluate the effects of different doses of PCS12852 on symptoms, as measured by the American Neurogastroenterology and Motility Society Gastroparesis Cardinal Symptom Index Daily Diary (ANMS GCSI-DD), in patients with moderate to severe idiopathic and diabetic gastroparesis	 Change from baseline in the ANMS GCSI-DD) (i.e., Day-7 to Day -1) (predose) and Day 7 (Day 1 to Day 7) Change from baseline in the ANMS GCSI-DD (i.e., Day-7 to Day -1) (predose) and Day 14 (Day 8 to Day 14) Change from baseline in the ANMS GCSI-DD (i.e., Day-7 to Day -1) (predose) and Day 21 (Day 15 to Day 21) Change from baseline in the ANMS GCSI-DD (i.e., Day-7 to Day -1) (predose) and Day 28 (Day 22 to Day 28) 			
To evaluate the effects of different doses of PCS12852 on symptoms or QOL, as measured by the PAGI-SYM, PAGI-QOL, PGI-S, PGI-C, CGI-S and CGI-I, in patients with moderate to severe idiopathic or diabetic gastroparesis	 Change from baseline in ANMS GCSI-DD score over time (Day 7, 14, 21, 28) by comparing Day 7 to Day 14, Day 14 to Day 21 and Day 21 to Day 28. Change from baseline in the sub scores (nausea, early satiety, postprandial fullness, upper abdominal pain and number of vomiting episodes) of the 			

Version 3.0 28 of 85 20 April 2022

Objectives	Endpoints
	ANMS-GCSI-DD over time (Day 7, 14, 21, 28) by comparing Day 7 to Day 14, Day 14 to Day 21 and Day 21 to Day 28.
	Change from baseline in PAGI-SYM and PAGI-QOL scores over time by comparing Day 1 to Day 28.
	Change from baseline in Clinical Global Impression-Severity (CGI-S) and Clinical Global Impression-Improvement (CGI-I) scores over time by comparing Day 1 to Day 28.
	Change from baseline in PGI-S and PGI-C scores over time by comparing Day 1 to Day 28.

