9.2.4 Other Patient-reported outcomes (PRO) Assessments – Exploratory Endpoints

The PAGI-SYM is a patient-reported outcome that asks patients the severity of their symptoms over the last 2 weeks. The PAGI-SYM was developed to measure symptom severity for gastroparesis, functional dyspepsia, and gastroesophageal reflux disease. The PAGI-SYM is composed of 20 items and 6 subscales: heartburn/regurgitation (7 items), nausea/vomiting (3 items), postprandial fullness/early satiety (4 items), bloating (2 items), upper abdominal pain (2 items), and lower abdominal pain (2 items). Subscale scores are calculated by averaging across items comprising the subscale; scores vary from 0 (none or absent) to 5 (very severe). The half-scale rule is applied for missing data (i.e., the subscale score is calculated by using the mean of non-missing items; when more than 50% of items are missing, the score is set to missing). The change from baseline in the PAGI-SYM will be analyzed using the same statistical approach as described for other analyses.

The PGI-C is a patient-reported questionnaire with a 7-point rating scale where the participant rates his/her own improvement in overall symptoms relative to the baseline assessment. It is rated as 1, very much improved; 2, much improved; 3, minimally improved; 4, no change; 5, minimally worse; 6, much worse; or 7, very much worse.

The PGI-S is a patient reported questionnaire with a single question to measure disease severity on a 5-point rating scale. It is rated as "none," "mild," "moderate," "severe," and "very severe."

Version 3.0 57 of 85 20 April 2022

The PAGI-QOL is a 30-item instrument assessing quality of life in patients with gastroparesis. The questionnaire covers 5 domains: Daily Activities, Clothing, Diet and Food Habits, Relationship, and Psychological Well-Being and Distress. The effect on overall quality of life and well-being over the past 2 weeks is rated on a scale of 0 (none of the time) to 5 (all of the time) for each item.

Clinicians complete the CGI-S, which is a 7-point scale on which the clinician rates the severity of the patient's gastroparesis at the time of assessment and refers to the degree of illness at the time of the visit and during the 2 weeks before the visit. The CGI-S is rated on the following 7-point scale: 1: normal, not at all ill; 2: borderline ill; 3: mildly ill; 4: moderately ill; 5: markedly ill; 6: severely ill; 7: among the most extremely ill patients.

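### CGI-S is a mental-illness rating in Section 8.1.3.2 but a gastroparesis rating in Section 9.2.4, and the change ratings CGI-I and PGI-C are specified as change from Day 1 (exploratory scales only)

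*Combined protocol and SAP*

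**What the plan says.** **CGI-S.** Section 8.1.3.2 introduces the scale as "severity of psychopathology from 1 to 7" and gives the investigator's question as "Considering your total clinical experience with this particular population, how mentally ill is the patient at this time". Its second anchor is "2=borderline mentally ill". On timing it says: "The rating is based upon observed and reported symptoms, behavior and function in the past 7 days". Section 9.2.4 describes the same 7-point scale as one on which "the clinician rates the severity of the patient's gastroparesis at the time of assessment", and adds that it "refers to the degree of illness at the time of the visit and during the 2 weeks before the visit". There the second anchor is "2: borderline ill". Table 2 (Section 3) places the scale under an objective about the effect of dose "on symptoms or QOL, as measured by the PAGI-SYM, PAGI-QOL, PGI-S, PGI-C, CGI-S and CGI-I", in gastroparesis patients.

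**CGI-I and PGI-C.** Sections 8.1.3.2 and 9.2.4 describe the CGI-I as the clinician's rating of change since treatment began. Section 9.2.4 describes the PGI-C as the patient's rating of improvement relative to baseline. Section 9.2.4 scores both from 1 to 7, with 4 meaning no change. The Synopsis, the Schedule of Activities and Section 4.1 have both completed at Visit 3 (Day 1). The Synopsis, Table 2 and Sections 8.1.3.2 and 8.1.3.3 specify the endpoint as change from baseline, Day 1 against Day 28.

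**Tier.** The Synopsis and the headings of Sections 8.1.3 and 9.2.4 label all four scales exploratory.

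**The concern.** Section 8.1.3.2 is the assessment section, the natural source for a rating form. A form built from it would collect a psychiatric severity rating, which is neither what Section 9.2.4 describes nor what the Table 2 objective needs. A later SAP can change how a score is analysed, but it cannot turn a mental-illness rating into a gastroparesis rating.

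For CGI-I and PGI-C, the specified endpoint is a change in a change rating. At best the subtraction is redundant; otherwise the result loses the meaning of its labels. Section 8.1.3.3 wants the PGI scales as anchors for interpreting meaningful within-patient change, and that use depends on the labels.

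**Working it through.** The protocol states no figure to reproduce on this point. The check is a comparison of text plus a count.

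**1. CGI-S side by side**

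| | Section 8.1.3.2 | Section 9.2.4 |
|---|---|---|
| Construct | Psychopathology | Gastroparesis severity |
| Anchor 2 | Borderline mentally ill | Borderline ill |
| Recall | Past 7 days | Visit and 2 weeks before |
| Basis of the Day 28 rating | About Days 22–28 | Days 14–28 (28 − 14 = 14) |

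At Day 28 both windows lie wholly on treatment, so for the endpoint the conflict concerns construct and window length. The Schedule of Activities also places the CGI-S at Visit 8 (Day 35), outside the endpoint. There the 7-day window is about Days 29–35, after the last planned dose, while the 2-week window is Days 21–35, part on and part off drug.

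**2. CGI-I and PGI-C with every Day 1 score equal to 4**

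The difference is d = Day 28 score − 4. Scores 1 to 7 map one-to-one to −3, −2, −1, 0, 1, 2, 3. Between any two arms, mean(Day 28 − 4) differs by exactly as much as mean(Day 28), so the subtraction adds nothing.

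Suppose the baseline-adjusted ANCOVA of the Synopsis were carried over to these scales, which the protocol does not state. With three arms of 8, the columns are an intercept, 2 arm terms, 1 type term and a Day 1 score that is always 4. That is 5 columns of rank 4, because the last is 4 times the intercept. The Day 1 coefficient cannot be estimated; the arm contrasts still can. Section 9.2.2 omits the type term, which leaves 4 columns of rank 3 and the same conclusion.

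**3. CGI-I and PGI-C with Day 1 free to vary**

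There are 7 × 7 = 49 pairs (Day 1, Day 28). A difference d arises from 7 − |d| pairs, for d from −6 to +6, which is 13 values. Check: 7 + 2 × (6 + 5 + 4 + 3 + 2 + 1) = 49.

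- d = −1 arises from 6 pairs: (2,1), (3,2), (4,3), (5,4), (6,5), (7,6). The Day 28 label runs from 1 (very much improved) to 6 (much worse).
- d = 0 arises from 7 pairs and covers all seven Day 28 labels.

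This counts what the endpoint could mean. It does not predict how often Day 1 scores will depart from 4.

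**4. Wording slips**

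Section 8.1.3.3 announces seven PGI-C answers but prints eight, with *much improved* twice; Section 9.2.4 lists seven. The CGI-I stem in Section 8.1.3.2 refers to study admission, which is undefined, while its labels refer to the start of study treatment.

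**The case against.** The strongest reply on the CGI-S is that Section 8.1.3.2 only describes the generic published instrument, that Section 9.2.4 supplies the disease-specific version, and that no rating form is in the documents. So nothing shows that psychiatric data would be collected. The last part stands: the harm depends on which text the form follows. But Section 8.1.3.2 states the question put to the investigator and ends with how the scale will be used in this study, so it cannot be read as background.

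On CGI-I and PGI-C, Day 1 is expected to be 4, in which case the specified contrast equals the Day 28 contrast. The text speaks of comparing two days without giving a formula, and no ANCOVA is stated for these scales. All of that is fair. It means that no bias or loss of precision has been shown and that the rank result is conditional. It does not justify specifying a baseline for a scale that already measures change from baseline, in every statement of the endpoint. The wording slips in step 4 are editorial, and the conclusion does not rest on them.

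**Conclusion.** The concern holds, as a minor one. The two CGI-S definitions cannot both be followed, and the one in Section 8.1.3.2 measures the wrong construct for the Table 2 objective. The CGI-I and PGI-C endpoints are mis-specified: harmless if Day 1 is always 4, hard to interpret if it is not. The Day 28 scores of both scales are usable as they stand.

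The documents give no values from which to size a loss of precision, and none is claimed. The practical weight of the CGI-S point rests on the unverified possibility that a form follows Section 8.1.3.2. The primary and secondary endpoints are unaffected.

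**What to change.** - **CGI-S:** in Section 8.1.3.2 adopt the Section 9.2.4 definition (severity of the patient's gastroparesis), remove the references to mental illness and psychopathology, and state one recall window in both sections. Keep change from Day 1 for CGI-S and PGI-S.
- **CGI-I and PGI-C:** in the Synopsis, Table 2 and Sections 8.1.3.2 and 8.1.3.3, define the endpoint as the Day 28 score compared between arms, with no Day 1 value of the same scale. This keeps the labels that the anchor use in Section 8.1.3.3 needs. The Day 1 ratings of these two scales then become unnecessary and may be dropped.
- **Wording:** tie the CGI-I stem and labels to one reference point, the start of study treatment, and print the seven PGI-C labels of Section 9.2.4 in Section 8.1.3.3.

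The cost is a text correction with no added assessment. The sponsor should check the CGI-S form. If it carries the Section 8.1.3.2 wording, the electronic form must change too, and any ratings already collected on it should be reported separately and not relabelled as gastroparesis severity.

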8.1.3.3 PGI-S and PGI-C

Consistent with the recommendations in the FDA Draft Guidance: Gastroparesis: Clinical Evaluation of Drugs for Treatment, 2019, multiple anchor scales will also be used to assess the impact of treatment on the patient's disease. The patient global impression of severity (PGI-S)

Version 3.0 48 of 85 20 April 2022

and patient global impression of change (PGI-C) scales will be used in the proposed Phase 2A study, with the intent of providing accumulated evidence to help interpret a clinically meaningful within-patient score change.

The PGI-S will assess the patient's severity of symptoms. The choices are: "none," "mild," "moderate," "severe" and "very severe."

The PGI-C will assess the patient's impression of how their GI symptoms have changed. The patient will choose 1 of 7 answers, including: "very much improved," "much improved," "much improved," "minimally improved," "no change," "minimally worse," "much worse" and "very much worse."

In this study, the change from baseline over time for the PGI-S and PGI-C scores will be assessed by comparing Day 1 to Day 28. The patients will complete these assessments using an electronic diary.

8.2 Safety Assessments

Planned timepoints for all safety assessments are provided in the SoA (Table 1).

- AEs (by type, severity, and relatedness) at each visit.
- Changes in safety clinical laboratory testing and vital signs at each site visit.
- Changes in ECGs at each site visit and the potential correlation of the PK with changes in the ECG.
- Change from baseline in the C-SSRS scores over time by comparing Day 1 to Day 28.

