1.2 Schedule of Activities (SoA)

 Table 1
 Schedule of Activities (SoA)

Procedure	Visit 1 (Screening)	Visit 2 (Screening) (Baseline)	Visit 3 (Randomization) Day 1	Visit 4 Day 7	Visit 5 Day 14	Visit 6 Day 28	Visit 7 48-72 hrs after Day 28 visit	Visit 8/ET Day 35
Visit Window	Days -	21 to -1		±2 days	+3 days	+1 day	_	±1 day
Informed consent	X							
Demographic information	X							
Medical history	X							
Inclusion/ Exclusion criteria	X	X	X					
Screening Lab testing (inc. Hep B/C, HIV and TB)	X							
Concomitant Medications	X	X	X	X	X	X		X
Vital signs	X	X	X	X		X		X
Physical exam ^g	X		X	X	X	X		X
¹³ C GEBT		X				X ^d		

Procedure	Visit 1 (Screening)	Visit 2 (Screening) (Baseline)	Visit 3 (Randomization) Day 1	Visit 4 Day 7	Visit 5 Day 14	Visit 6 Day 28	Visit 7 48-72 hrs after Day 28 visit	Visit 8/ET Day 35
Visit Window	Days -	21 to -1		±2 days	+3 days	+1 day		±1 day
ANMS GCSI-DD ^a		X	X	X	X	X		
Safety laboratory testing				X		X		X
Pregnancy test ^b	X		X	X	X	X		X
ECG ^h	X		Xi	X ^j	Xj	X		X e
C-SSRS	X		X	X	X	X		X
PGI-S			X			X		X
PGI-C			X			X		X
PAGI-SYM			X			X		
PAGI-QOL			X			X		
CGI-S			X			X		X
CGI-I			X			X		X
Adverse Events	X	X	X	X	X	X		X
Study Drug Dispensed			X	X	X	X		

Procedure	Visit 1 (Screening)	Visit 2 (Screening) (Baseline)	Visit 3 (Randomization) Day 1	Visit 4 Day 7	Visit 5 Day 14	Visit 6 Day 28	Visit 7 48-72 hrs after Day 28 visit	Visit 8/ET Day 35
Visit Window	Days -2	21 to -1		±2 days	+3 days	+1 day		±1 day
Study Drug Instructions	X	X	X					
Study Drug Administered			X			X ^c		
PK sample ^f			X			X	X^k	
Drug Accountability				X	X	X		

- a. ANMS GCSI-DD will be collected for 7 consecutive days after Screening Visit 2, but prior to randomization (i.e. from Days -7 to -1) as well as from Day 1 to Day 28.
- b. For WOCBP: Serum β-HCG at Screening Visit 1; Urine pregnancy test at subsequent visits
- c. Patients will take the dose of PCS12852 or placebo in clinic on Day 28.
- d. A blood glucose finger stick will be taken both before and at the completion of the GEBT.
- e. Repeat ECG at Visit 8, only if ECG at Visit 6 was abnormal.

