- f. PK blood samples will be drawn at both Visit 3 (Day 1) and Visit 6 (Day 28) at the following timepoints: pre-dose (trough) and at 0.5h, 1h, 2h, 4h, 6h and 8h post dose. Clinical staff are encouraged to take the blood samples for PK analysis at the scheduled time point; however, deviations from the scheduled sample times are not considered protocol deviations. The exact time and date of the blood draw must be recorded.
- g. A symptom driven physical exam will be done on Visit 3 (Day 1), Visit 4 (Day 7), Visit 5 (Day 14) and Visit 8 (Day 35).
- h. Clinical staff are encouraged to perform ECGs prior to any blood draws at a given visit.
- i. ECGs should be performed prior to the 4 hour PK draw.
- j. ECGs should be performed approximately 4 hours after patient's dose.
- k. The single PK sample drawn between 48-72 hours after the Day 28 visit can either be done in the office or by a home health nurse.

2 Introduction

Gastroparesis is a disorder characterized by delayed gastric emptying of solid food in the absence of a mechanical obstruction, particularly pyloric stenosis (Camilleri, 2013). This delay may result in the cardinal symptoms of early satiety, postprandial fullness, nausea, vomiting, belching and bloating. The syndrome is caused by neuromuscular dysfunction that leads to delayed gastric emptying (Camilleri, 2018).

Gastroparesis can be idiopathic, associated with diabetes mellitus, can occur after a medical intervention (iatrogenic or post-surgical), may be associated with neurological disorders or may occur after a bacterial or viral infection. In one series of 146 patients, the etiology of gastroparesis was 36% idiopathic, 29% diabetic, 13% postsurgical, 7.5% Parkinson's Disease, 4.8% collagen vascular disorders, 4.1% intestinal pseudo obstruction and 6% miscellaneous (Soykan, 1998). The majority of patients (up to 80%) with gastroparesis are women (Parkman, 2019).

The symptoms of gastroparesis are nonspecific and may mimic other disorders such as functional dyspepsia.

Treatment of symptomatic gastroparesis generally follow these principles (Quigley, 2001):

- 1. Dietary recommendations to correct fluid, electrolyte or nutritional deficiencies;
- 2. Identify and rectify the underlying cause of gastroparesis, if possible; and
- 3. Reduce the symptoms of gastroparesis.

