Patients will return to the site for Day 1 (Visit 3 [Randomization]) where patients who meet the criteria for having moderate to severe symptoms based on the ANMS GCSI-DD will be randomized in a 1:1:1 ratio into three treatment groups, PCS12852 0.1 mg, PCS12852 0.5 mg or placebo. At Visit 3, patients will answer a series of questionnaires including the Patient Assessment of Gastrointestinal Disorders Symptom Severity Index (PAGI-SYM), Patient Assessment of Upper Gastrointestinal Disorders – Quality of Life (PAGI-QOL), Patient Global Impression of Severity (PGI-S) and the Patient Global Impression of Change (PGI-C). Patients will arrive in a fasted condition and have PK samples drawn prior to receiving the first dose and at the following times after the first dose, 0.5, 1, 2, 4, 6, and 8 hours. The ECG should be performed prior to the 4-hour PK draw between the 2- and 4-hour samples. The investigator will assess the patient through the C-SSRS as well as the CGI-S and CGI-I.

Patients will return to the site on Day 7 (Visit 4) and Day 14 (Visit 5) to undergo safety and tolerability assessments as per the Schedule of Assessments, along with the investigator assessing the patient for the C-SSRS to ensure the patient does not have any suicidal tendencies

Version 3.0 30 of 85 20 April 2022

or ideation. Sites will be asked to schedule the patient's visit so that the ECG can be performed approximately 4 hours after the patient's dose.

Patients will take their assigned treatment once daily for 28 days and will return to the site on Day 28 (Visit 6) for their final dose. On Visit 6, PK samples will be drawn and the GEBT will be repeated. During the treatment period, the patients will also complete the ANMS GCSI-DD. Each patient will be told to take one tablet from their assigned kit each day at approximately the same time each morning, at least 30 minutes prior to a meal (actual dosing times will be captured via a dosing diary), while fasting starting on Day 1 for 28 days.

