8.2.1 Physical Examinations

Complete physical examinations (excluding pelvic exam in women and genital exam in men, and rectal exam in both genders) are to be performed at Screening (Visit 1) and Day 28 (Visit 6). Symptom-directed (abbreviated) physical examinations may be conducted as required at Visit 3 (Day 1) Visit 4 (Day 7), Visit 5 (Day 14), and Visit 8 (Day 35).

Patients should be weighed with no shoes, in light clothing, without any outerwear. Height should be measured only at the first study visit. Any abnormality noted on the physical examination done at or following Visit 3 or the early termination visit that was not present on the physical examination at screening should be reported as an AE if considered by the Investigator to be clinically significant.

Version 3.0 49 of 85 20 April 2022

Investigators should pay special attention to clinical signs related to previous serious illnesses.

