8.2.2 Vital Signs

- Heart rate (HR), respiratory rate, systolic and diastolic blood pressure (BP), weight and temperature will be assessed; the method for measuring temperature will be per the site's preference.
- BP and HR measurements will be assessed in the sitting position with a completely automated device. Manual techniques will be used only if an automated device is not available.
- BP and HR measurements should be preceded by at least 3 minutes of rest for the patient in a quiet setting without distractions (eg, television, cell phones).
- Vital signs are to be taken before blood collection for laboratory tests.

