8.2.3 Electrocardiograms

A 12-lead ECG will be obtained as outlined in the SoA (Table 1) using an ECG machine after the patient has rested for 5 minutes in supine position. At Visit 3 (Randomization) and Visit 6 (Day 28), the ECG will be performed prior to the 4-hour PK draw. At Visit 4 and Visit 5, the ECG will be performed approximately 4 hours after the patient's dose. The Investigator will report whether the ECG is normal or abnormal and if the result is considered clinically significant or not.

All clinically significant ECG abnormalities occurring during the study should be documented as AEs. The ECG performed at Screening will be recorded as the baseline assessment. Standard ECG parameters, including heart rate, QRS, PR, QT, Bazett's correction for QT (QTcB), and Fridericia's correction for QT (QTcF) intervals will be measured. The ECGs will be overread by the Investigator to assess any abnormalities.

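### Vital signs are a safety endpoint at every site visit, but none are scheduled on Day 14; one tick in Table 1 would add a second interim reading at little cost

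*Combined protocol and SAP*

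**What the plan says.** The safety endpoint reads "Changes in safety clinical laboratory testing and vital signs at each site visit" and appears in the Synopsis, in Table 2 and in Section 8.2. Section 8.2 opens by sending the reader to Table 1 for the timing of every safety assessment. The Synopsis also lists safety and tolerability among the primary objectives.

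Table 1 schedules vital signs at Visits 1 to 4, 6 and 8, and leaves Visits 5 and 7 blank. The row "Safety laboratory testing" is marked only at Visits 4, 6 and 8.

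Visit 5 is attended in person. Section 4.1 has patients return on Day 7 and "Day 14 (Visit 5) to undergo safety and tolerability assessments as per the Schedule of Assessments". Table 1 gives that visit an ECG, a physical exam, the C-SSRS, a pregnancy test and adverse event collection.

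Section 8.2.2 defines the measures: "Heart rate (HR), respiratory rate, systolic and diastolic blood pressure (BP), weight and temperature will be assessed". Blood pressure and heart rate are taken sitting, normally by automated device, after at least 3 minutes of rest. Section 8.2.3 covers the ECG, taken supine after 5 minutes of rest: "Standard ECG parameters, including heart rate, QRS, PR, QT" and the corrected QT intervals are measured. For the Day 14 exam, Section 8.2.1 says: "Symptom-directed (abbreviated) physical examinations may be conducted as required".

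**The concern.** The endpoint wording leads a reader to expect a vital-sign change from baseline at Day 14, and the schedule does not provide for one. The visit is already a safety visit and includes an ECG, so the omission saves little.

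What is at stake is modest. With about 8 patients per arm, the descriptive safety summary has a single interim set of vital signs, on Day 7, and then nothing scheduled until the last dose on Day 28. Section 2.2 lists diarrhea and nausea among the most frequent treatment-emergent events in Phase 1. Weight and blood pressure are objective measures that bear on fluid loss, and diarrhea is not an item in the daily symptom diary.

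**Working it through.** No figure in the plan needs reproducing here. The check compares the schedule with the endpoint wording and counts days.

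**Is the blank cell real?** The vital-signs row in Table 1 has one entry per column: the procedure name plus eight visits. The physical-exam row has the same number of fields and is marked at Visit 5, so the blank is not a shift from text extraction.

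**What Table 1 schedules from first dose onward**

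| | V3, Day 1 | V4, Day 7 | V5, Day 14 | V6, Day 28 | V7, PK only | V8, Day 35 |
|---|---|---|---|---|---|---|
| Vital signs | yes | yes | **no** | yes | no | yes |
| Safety labs | no | yes | no | yes | no | yes |
| ECG | yes | yes | yes | yes | no | only if V6 abnormal |
| Physical exam | yes | yes | yes | yes | no | yes |
| C-SSRS | yes | yes | yes | yes | no | yes |
| Adverse events | yes | yes | yes | yes | no | yes |

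Visit 7 is a single PK sample that "can either be done in the office or by a home health nurse", so its blank cell needs no repair.

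**Visit windows (Table 1).** Visit 4 is Day 7 ±2, so Days 5 to 9. Visit 5 is Day 14 +3, so Days 14 to 17. Visit 6 is Day 28 +1, so Days 28 to 29.

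**Longest gap now (Visit 4 to Visit 6)**
- Nominal: 28 − 7 = 21 days; 21/28 = 75% of the treatment period.
- Shortest: 28 − 9 = 19 days; 19/28 = 68%.
- Longest: 29 − 5 = 24 days; 24/28 = 86%.

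**Gaps with vital signs at Visit 5**
- Visit 4 to Visit 5: nominal 14 − 7 = 7 days; range 14 − 9 = 5 to 17 − 5 = 12 days.
- Visit 5 to Visit 6: nominal 28 − 14 = 14 days (14/28 = 50%); range 28 − 17 = 11 to 29 − 14 = 15 days (39% to 54%).
- The longest gap therefore falls from 21 to 14 days nominally, and from 24 to 15 days at most.

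**What Day 14 yields now.** Section 8.2.2 lists six measures: heart rate, respiratory rate, systolic pressure, diastolic pressure, weight and temperature. None is scheduled on Day 14 in the form that section describes. The ECG gives a heart rate, but supine rather than sitting. Weighing instructions sit under physical examinations in Section 8.2.1, so a weight may be taken if an exam is done, but the Day 14 exam is symptom-directed and no weight is scheduled.

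**The case against.** The strongest reply is that the endpoint does not demand a Day 14 value. Section 8.2 puts Table 1 in charge of timing before it lists the endpoints, and the each-site-visit wording is loose elsewhere. It is applied to ECGs too, although Table 1 has none at Visit 2 and repeats the Visit 8 ECG only after an abnormal one at Visit 6. The same endpoint sentence covers laboratory tests, which are likewise not scheduled at Visit 5. If rewording cures the laboratory mismatch, it cures the vital-sign mismatch as well. This stands: the wording alone does not make the tick necessary.

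The blank may also be deliberate. After Day 1, vital signs are scheduled at exactly the visits with safety laboratory tests (4, 6 and 8), so Visit 5 may be meant as a lighter visit centered on the ECG, C-SSRS and adverse events. The documents neither state this nor rule it out, so a reader should not infer a forgotten tick.

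The clinical case is thin. Section 2.2 reports no vital-sign changes in Phase 1. Section 4.3 describes multiple doses up to 3 mg daily, six times the top dose here (3/0.5), as generally well tolerated. Visit 4 falls at about steady state, which Section 2.1 places at approximately Day 5. Nausea and vomiting are recorded daily, rescue use is recorded, and unscheduled safety samples are allowed. No section sets a maximum interval between vital-sign readings. All of this stands and keeps the severity low.

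What survives is the practical argument. Vital signs need no blood draw, so the burden that might explain omitting laboratory tests on Day 14 does not apply to them.

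**Conclusion.** The point holds as a cheap, low-severity improvement. Table 1 omits vital signs at an attended safety visit, which leaves 21 days nominally (19 to 24 with windows) between scheduled on-treatment readings. One added reading brings that to 14 days, and 15 at most. The day counts assume visits fall within the Table 1 windows.

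Three stronger readings are tempting, and the documents do not support them:
- A reader might infer that the safety endpoint fails or that sites lack clear instructions. Table 1 governs conduct, vital signs are summarized descriptively under Section 9.2.5, and neither the primary analysis nor the cardiac stopping rule depends on a Day 14 value.
- A reader might infer that the trial has no mid-treatment blood pressure or weight. Visit 4 provides both on Day 7; what is missing is a second interim reading.
- A reader might count the ECG heart rate as one of the six vital signs already obtained on Day 14. It is taken supine, whereas Section 8.2.2 calls for a sitting measurement, so it is a related value and not a substitute.

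**What to change.** Tick vital signs at Visit 5 in Table 1. The cost is a few minutes of staff and patient time at an existing visit, with no extra visit, staff or blood draw. Section 8.4 says that adding time points for planned assessments, once documented and approved, is not a protocol amendment. That sentence sits under the pharmacokinetics heading, so the sponsor should confirm that it applies to vital signs.

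As an optional consistency edit, replace the reference to each site visit in the Synopsis, Table 2 and Section 8.2 with a reference to the visits scheduled in Table 1. This covers the laboratory tests, which stay unscheduled at Visit 5, and avoids implying anything for Visit 7. The laboratory schedule need not change.
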